N=150). In the same pilot trial, 77% of subjects completed the 8 week trial; we anticipate similar retention in the proposed study. Thus, a randomized sample size of 100 participants per treatment arm (total N=200) would maintain power to detect the clinically significant difference stated above in the presence of ~25% attrition during the study. Similarly, in the same pilot study, reductions in craving were significantly greater in the NAC vs. placebo treated group ($\Delta=3.0$ vs. $\Delta=1.3$). The randomized sample size of 100 per treatment arm provides >95% power with a type 1 error rate of 5% to detect this effect in the presence of 25% attrition during the study period. It is hypothesized that NAC reduces the risk of drinking as compared to placebo. With this stated sample size, a 25% decreased risk in the consumption of standard drinks can be detected with at least 80% power between the NAC and placebo treated arms (Risk Ratio=0.75).

Power calculations for the neuroimaging component are based on previous studies of individuals with PTSD or substance use disorders. Based on our previous work and the extant literature, we conservatively estimate ~70% of participants (140/200) will be eligible and volunteer for the neuroimaging component. A recent study of 29 individuals (PTSD=14, controls=15) observed significant differences in PFC-AMY resting state connectivity⁵⁰. The effect size for this difference was 0.8 (Cohen's d). Thus, power (1- β) reaches .80 with a total sample size of N=26 (two-tailed, alpha=.05). Another study of 45 cocaine-dependent individuals found that individuals who relapsed (n=24) had significantly lower PFC-AMY connectivity at baseline as compared to individuals who did not relapse (n=21)⁴⁹. The effect size for this reduction was 1.0. Thus, power (1- β) reaches .80 with N=34 subjects (two-tailed, alpha=.05). For exploratory hypothesis 4, the only published study of NAC effects on brain glutamate found that one dose of NAC vs. placebo administered 1 hour prior to scanning, led to a significant modification in ACC glutamate with an effect size of $d = 2.6$ in individuals with cocaine dependence. Although the present study will be examining the effects of chronic NAC treatment in individuals with AUD and PTSD, an effect of similar magnitude would provide power > 0.99. The present study is therefore well-powered to test the proposed hypotheses.

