Hypotheses. The hypotheses and statistical approaches for testing each hypothesis are listed below.

Hypothesis 1: NAC treatment will result in significantly greater reduction in AUD severity and craving, as compared to placebo. To test this hypothesis, a mixed effects modeling framework will be specified with the total number of standard drinks consumed and the OCDS total score as the primary outcomes. A Poisson distribution will be assumed with a logarithm link function to assess the effects of NAC treatment and the baseline number of total standard drinks (past 60 days) prior to treatment entry. Over-dispersion due to a wider than expected distribution in discrete count models (from heterogeneity) can have a significant impact on parameter inference, thus when detected, a negative binomial (NB) distribution will be specified. Further, data collected in substance abuse studies often contain a preponderance of zeros, and these zeros in the distribution can be considered sampling zeros in the Poisson process¹²⁵. If this excess is present in the distribution, two-part Hurdle models (Poisson and NB) will be explored¹²⁶⁻¹²⁷. The hurdle part of the model will allow us to estimate the probability of abstinence during the study period (as an odds ratio) while the Poisson/NB portion will allow for the assessment of the risk of an increase in using days beyond zero during the study period (as a risk ratio). Model fit of the Poisson (Hurdle Poisson) model will be compared to the Negative Binomial (Hurdle NB) model by practical examination of the deviance and Pearson chi-square values (Likelihood Ratio) with respect to their degrees of freedom. Baseline alcohol use and craving will be included in pertinent models as covariates. Additional alcohol use outcomes will be assessed: percentage of drinking days (DD) and the number of heavy drinking day (HDD). End of study abstinence will be assessed using logistic regression models. DD and HDD will be assessed using count models.

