For hypotheses 3A and 3B, the following preprocessing and analytical parameters will be used. Preprocessing: Post-acquisition preprocessing and statistical analysis of imaging data will be performed using FEAT (FMRI Expert Analysis Tool) Version 5.98, part of FSL (FMRIB's Software Library). Data will be preprocessed using scripting tools from FEAT. Non-brain signal will be removed using FSL's BET brain extraction. Scans will be corrected for motion using FSL's linear registration and scans will be spatially smoothed using a Gaussian kernel of 8 mm FWHM. Participants with head motion ≥ 0.2 mm will be excluded from the analyses¹²⁷. Motion artifacts will be identified and scrubbed from each subject's data. Scans will be spatially co-registered with a standardized anatomical template (Montreal Neurological Institute) using a 12 parameter affine transformation. Analysis: Functional connectivity will be measured using a psychophysiologic interaction seed-based approach¹²⁹⁻¹³⁰. PPI analysis is used to assess the functional coupling between different brain regions. The PPI is defined as the change in connectivity of one area (i.e., the seed region) to another in relation to the experimental context (e.g., alcohol vs. neutral cues). PPI analyses for resting state, trauma and alcohol cues will be performed separately. Customized sq. wave forms representing the trauma run (1=trauma block and -1=neutral block) and the alcohol cue run (1=alcohol block and -1=neutral block) the duration of each block will be convolved with a double-gamma hemodynamic response function. A mask of the seed region will be made using a 12-mm diameter sphere located in the center of the AMY using the MNI coordinates (x, y, z = ± 22 , 0, -22). The transformation parameters described above will also be applied to the mask. For each subject, the mean corrected and high pass filtered time series of the BOLD signal in the AMY will be extracted and used in a single subject whole brain PPI analysis. The PPI model will include the task vector, time series of the BOLD signal in the AMY, a term representing the positive task x seed interaction, and a term representing the negative task x seed interaction. The first level analysis will generate contrast images of the parameter estimates for each of the four regressors. Voxels will be thresholded at $Z > 2.3$ using a corrected cluster threshold of $p = 0.05$. The contrast images of the parameter estimates of the positive and negative task x seed interactions will be combined for group-level t-tests to identify regions that exhibited altered connectivity with the AMY during the trauma and alcohol cues as compared to neutral cues. All group-level results will be thresholded at $Z > 2.3$ using a corrected cluster threshold of $p = 0.05$. Separate linear regression tests will be used to test for associations between PFC-AMY connectivity at baseline and improvement in AUD and PTSD symptoms during treatment. Changes in total standard drinks will be regressed against the parameter estimate obtained from the center voxel from each cluster that exhibited a significant task x seed interaction with the AMY at rest and in response to the alcohol cues (Hypothesis 3A). Changes in CAPS-5 total scores will be regressed against the parameter estimate obtained from the center voxel from each cluster that exhibited a significant task x seed interaction with the AMY at rest and in response to the trauma cue (Hypothesis 3B). Further exploratory analyses will examine change in PFC-AMY connectivity from pre- to post-treatment and associations with alcohol and PTSD outcomes, both within and between medication groups.

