
Exploratory Hypothesis 4: NAC treatment will be associated with a significant change in ACC glutamate concentrations, as compared to placebo. Change in ACC glutamate concentrations will be associated with alcohol and PTSD outcomes.

Analysis of PRESS data will be conducted using LC Model 6.3¹³¹, an operator-independent curve-fitting software package that uses least-squares estimation for quantifying metabolite concentrations; the basis set for TE = 40ms is provided by the vendor and includes a number of metabolites including glutamate, creatine, glutamine, N-acetylaspartate, and phosphocholine. Only metabolites with fitting uncertainties (Cramer-Rao Lower Bound values) $< 20\%$ of SD in the LC Model output will be retained for analysis. LC Model includes standardized zero filling, Fourier transformation, and automated phase, baseline and eddy current correction. To address variability in within-voxel tissue composition we will extract and segment T₁-weighted images into partial volume maps of gray matter (GM), white matter (WM), and CSF using FSL tools, match the coordinates and size of the ¹H-MRS voxel with the segmented images and extract the tissue fractions within the voxel, correct the raw values obtained from the LC model (scaled

to water) for CSF and coil loading, and calculate each participant's GM to brain matter (GM/[GM+WM]) ratio for use as a covariate in the analyses. Change in glutamate levels will be analyzed as a mixed model (SAS PROC MIXED) with time as a within subject variable and medication group as between subject variables. Variables known to influence ACC glutamate levels (e.g., age, smoking status, tissue composition) will be considered as covariates. Further exploratory regression analyses will examine associations between glutamate difference scores and clinical outcomes (e.g., change in total standard drinks and CAPS-5 score) both within and between medication groups.

Summary: The proposed study will answer important questions regarding the potential of NAC as an effective pharmacotherapy for AUD and comorbid PTSD, and elucidate possible mechanisms underlying improved outcomes. The findings from this study have the potential to significantly improve the standard of patient care and accelerate research on the treatment of AUD and co-occurring PTSD

REFERENCES

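### Hypothesis 3A regresses change in drinks linearly, without a baseline-drinks term or the count framework of Hypothesis 1, and so probably loses efficiency

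*Combined protocol and SAP*

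**What the plan says.** All references are to the Statistical Analyses section of the combined protocol and SAP.

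- **Hypotheses 3A and 3B, Analysis.** Separate linear regressions relate baseline connectivity to improvement. For 3A: "Changes in total standard drinks will be regressed against the parameter estimate obtained from the center voxel" of each cluster with a significant interaction. No covariate, link, transformation or residual check is named.
- **Hypothesis 1.** Total standard drinks are modelled as Poisson with a log link, with the 60-day baseline count in the model. The plan warns: "Over-dispersion due to a wider than expected distribution in discrete count models (from heterogeneity) can have a significant impact on parameter inference". It moves to a negative binomial model if over-dispersion is detected. It also notes that "data collected in substance abuse studies often contain a preponderance of zeros", and it will explore hurdle models if that excess is present.
- **Hypothesis 2.** Residual checks and transformation are planned, but for the PTSD model only.
- **General.** Baseline characteristics associated with the primary outcomes become covariates. Whether this rule reaches Hypothesis 3A is not said.
- **Exploratory Hypothesis 4.** Exploratory regressions will examine "associations between glutamate difference scores and clinical outcomes (e.g., change in total standard drinks and CAPS-5 score"). The type of regression is left open.
- **Power and Sample Size.** The nearest basis for 3A is a comparison of relapse groups in cocaine dependence: "individuals who relapsed (n=24) had significantly lower PFC-AMY connectivity at baseline as compared to individuals who did not relapse (n=21"). No power is given for a regression on change in drinks.

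**The concern.** The same drinking measure is handled in two ways. Hypothesis 1 works on the log scale, conditions on baseline and says what happens if the counts are over-dispersed or have many zeros. Hypothesis 3A has none of these provisions.

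Two features of a raw change score can cost efficiency. First, without baseline in the model, differences in how much people drank at entry go into the residual. An abstainer's change is simply minus the baseline value, so part of the outcome is baseline itself. Second, the spread of a raw change tends to grow with drinking level, so a few very heavy drinkers can dominate the slope.

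At stake is the drinking half of Aim 3: a real prognostic association between connectivity and drinking could be missed.

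**Working it through.** **1. The plan's own figure.** The relapse comparison has the stated effect "The effect size for this reduction was 1.0", and power "reaches .80 with N=34 subjects (two-tailed, alpha=.05"). A two-sample t-test with d = 1.0 and two-sided alpha 0.05 needs 16.7, so 17 per group and 34 in total; power there is 0.807. The figure reproduces. (The companion claim for d = 0.8, "reaches .80 with a total sample size of N=26", does not reproduce as a total: 26 is the number per group, 52 in total. That is a separate matter.)

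**2. What that effect would imply if it carried over.** With groups of 24 and 21, r = d / √(d² + (n₁+n₂)²/(n₁n₂)) = 1 / √(1 + 2025/504) ≈ 0.45. With 140 imaged and 77% retained, n = 140 × 0.77 ≈ 108. Fisher's z gives power Φ(atanh(r)·√(n−3) − 1.96) = 0.998. If raw change were only 50% efficient (r multiplied by √0.5), power is 0.92; at 30% efficiency it is 0.72. The smallest r detectable with 80% power at n = 108 is 0.27.

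**3. Power of the competing models.** The documents give no drink distribution, dispersion or proportion of zeros, so the following are assumptions: n = 140 × 0.75 = 105; lognormal 60-day baseline with CV 0.7-1.0; negative binomial dispersion 0.4-0.8; drinks halved on average; log-rate slope 0.25 per SD of connectivity (e^0.25 = 1.28, hence 28%); no excess zeros. There were 400 simulated trials per setting, so the Monte Carlo standard error is at most √(0.25/400) = 0.025.

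| CV / dispersion | Linear, raw change | Linear + baseline | Negative binomial + log baseline | Share of gap closed by baseline |
|---|---|---|---|---|
| 0.7 / 0.4 | 0.66 | 0.90 | 0.98 | 24 of 32 points |
| 0.7 / 0.8 | 0.49 | 0.64 | 0.82 | 15 of 33 |
| 1.0 / 0.4 | 0.51 | 0.84 | 0.97 | 33 of 46 |
| 1.0 / 0.8 | 0.39 | 0.55 | 0.77 | 16 of 38 |

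Repeat runs widen the ranges to 0.34-0.66, 0.50-0.90 and 0.74-0.98. At slope zero, rejection rates were 0.03-0.07 for all three models.

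Adding baseline to the linear model closes 42-75% of the gap. Scale and distribution account for the remaining 8, 18, 13 and 22 points.

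**4. Wider assumptions.** With n = 108, mean baseline 300 drinks, log-SD of baseline 0.3-1.0, dispersion 0.3-1.2, 0-30% added zeros and slope 0.3 (1,000 trials per setting), power was 0.19-0.84 for raw change, 0.44-0.995 with baseline added, and 0.77-1.00 for negative binomial with log baseline. The loss from raw change against negative binomial was 13 to 58 points; with baseline in the linear model it was about 0 to 33. The negative binomial rejected up to about 7% under the null in the most dispersed settings, so its advantage there is slightly overstated.

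**5. Additive effect.** If connectivity shifts drinks by a fixed number (0.3 SD of the noise), linear regression with baseline reached 0.81-0.84, negative binomial 0.73-0.83, and raw change without baseline 0.27-0.69.

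**6. Many zeros.** With 30% zeros unrelated to connectivity added to the settings of step 3, a plain negative binomial model with model-based standard errors had power 0.16-0.18, against 0.31-0.52 for baseline-adjusted linear regression. Robust standard errors on the negative binomial gave 0.48-0.74. In step 4 the zeros depended on connectivity and the standard errors were rescaled for lack of fit; there, with 30% zeros, the negative binomial reached 0.77-0.88 and a hurdle model 0.66-0.82. So a count model helps with excess zeros only if its standard errors or its structure allow for them.

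**The case against.** The strongest defence is that nothing here is invalid. Type I error stays near nominal, and if the effect behind the plan's power statement carried over, power would exceed 0.9 even at half efficiency. The first part stands. The second is only conditional: that effect is a difference in connectivity between two relapse groups in another disorder, not a slope on change in drinks.

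A second defence is that the simulations favour the count model because they generate data from it with a multiplicative effect. This also stands in part. The risk ratio of 0.75 in the power section is a treatment effect and does not show that connectivity acts proportionally. Under an additive effect the baseline-adjusted linear model is as good or better. The model as written, without baseline, remains weaker in either case.

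A third defence is that the general covariate rule might bring baseline drinks into 3A. It might, but the text does not say so.

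Some stronger readings are tempting and not supported:

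- A reader might infer that the plan declares drinks over-dispersed and zero-heavy. Hypothesis 1 treats both as contingencies and gives no values. A zero on treatment is also not a spike at zero in a change score.
- A reader might infer that the problem is only distribution and scale. The working shows that the missing baseline term is often the larger part.
- A reader might infer that Hypothesis 4 uses least squares for drinks. That term there describes the spectral fitting.
- A reader might infer that switching to a plain negative binomial model is enough. With many unrelated zeros it can do worse than baseline-adjusted linear regression.

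**Conclusion.** The inconsistency is plain in the text: Hypothesis 3A drops the baseline term, log scale and safeguards that Hypothesis 1 gives the same measure, and offers no diagnostics in their place. The likely consequence is lost efficiency, not false positives.

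The size cannot be derived from the documents. Under the assumptions in step 3, raw change gives power of about 0.34-0.66, against 0.50-0.90 with baseline and 0.74-0.98 for the count model with log baseline. The full contrast between the first and last ranges should not be attributed to the choice of distribution, because it changes model and covariate together. That the count model beats the baseline-adjusted linear model depends on a multiplicative effect and on proper handling of any excess zeros. That adding baseline helps the linear model held in every powered setting run.

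Severity is low to moderate.

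**What to change.** In the analysis text for Hypothesis 3A, state that:

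- the outcome is on-treatment total standard drinks, adjusted for baseline drinks (log baseline in the count model), with connectivity as predictor;
- the Hypothesis 1 count framework applies in full: log link, negative binomial if over-dispersed, and the hurdle branch or robust standard errors if zeros are in excess;
- the result is reported as a rate ratio per SD of connectivity;
- linear regression adjusted for baseline drinks is a sensitivity analysis.

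Apply the same wording to the exploratory drinking associations in Hypothesis 4, with glutamate change as predictor.

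The cost is a few sentences and slightly more analysis work. No data collection changes. The effect is read as a ratio instead of a difference in drinks; the sensitivity analysis still supplies the latter.

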Next, participants will be asked to relax and keep their eyes opened and fixed on a cross-hair for six-minutes while resting state data are collected. Following this, participants will be exposed to alcohol, trauma and neutral cues. We will use a block design consisting of two 6-minute runs. During the alcohol cue run, participants will hear an audio recording describing in detail the last time they consumed alcohol. The alcohol cue run will be divided into two, 3-minute blocks of alcohol and neutral cues. During the trauma cue run, participants will hear an audio recording describing in detail their traumatic event. The trauma cue run will be also divided into two, 3-minute blocks of trauma and neutral cues. During the neutral cue run, participants will hear an audio recording describing something neutral, such as their typical morning routine. To minimize potential carry-over effects, the runs will be counterbalanced so that half of the subjects in the placebo group and half of the subjects in the NAC group are exposed to the alcohol cue first and the remaining participants in each group are exposed to the trauma cue first. T2*-weighted gradient-echo planar images (EPI) will be acquired with the following parameters: TR = 2000 ms, TE = 27 ms, flip angle = 76°, matrix 64 x 64, field of view = 23 cm, slice thickness = 3.7 mm with no gap, with 36 slices to cover the entire brain.

Subject Compensation. Subjects will receive \$50 for the baseline visit (plus \$25 bonus for showing up on schedule), \$25 for the medication initiation (randomization) visit, \$40 for completing each of the subsequent weekly visits during the treatment phase, and \$100 for the 3-month, \$100 for the 6-month, and \$100 for the 12-month post-treatment follow-up visits. Patients will also receive a \$25 bonus after completing the WK 6 and a \$60 bonus for completing WK 12 visit. Participants may also be eligible to participate in the optional MRI portion of the study. The participant may receive \$25 for script development, \$75 for the first neuroimaging visit and \$125 for the second neuroimaging visit. Compensation is available in the form of cash or check. Thus, the total amount subjects may receive for study participation is \$1190

STATISTICAL ANALYSES

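### Hypotheses 3A and 3B take their resting-state predictor from a task-by-seed interaction, but the resting run has no task, so that predictor is undefined as written

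*Combined protocol and SAP*

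**What the plan says.** All references are to the combined protocol and SAP.

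- **Hypotheses 3A and 3B** (Statistical Analyses, Hypotheses). Each names connectivity at rest as a predictor alongside connectivity under cues. The outcome is reduction in total standard drinks for 3A and in CAPS-5 for 3B.
- **Resting run** (Neuroimaging Component). Participants keep their eyes "fixed on a cross-hair for six-minutes while resting state data are collected". No blocks or conditions are described. The two cue runs are each split into 3-minute cue and neutral blocks.
- **Definition of PPI** (analysis text for 3A and 3B). "The PPI is defined as the change in connectivity of one area (i.e., the seed region) to another in relation to the experimental context".
- **Runs it applies to.** "PPI analyses for resting state, trauma and alcohol cues will be performed separately".
- **Task vectors.** "Customized sq. wave forms representing the trauma run (1=trauma block and -1=neutral block) and the alcohol cue run" are specified, the latter with the same 1/-1 coding. None is given for rest.
- **First-level model.** One model is described, with four regressors: the task vector, the amygdala time series, and a positive and a negative task-by-seed term. "The first level analysis will generate contrast images of the parameter estimates for each of the four regressors".
- **Group tests.** The interaction images go into group t-tests "to identify regions that exhibited altered connectivity with the AMY during the trauma and alcohol cues as compared to neutral cues". No resting contrast is described.
- **Outcome regressions.** The predictor is the centre-voxel estimate from each cluster that "exhibited a significant task x seed interaction with the AMY at rest and in response to the alcohol cues (Hypothesis 3A" or, for the other hypothesis, "exhibited a significant task x seed interaction with the AMY at rest and in response to the trauma cue (Hypothesis 3B".

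**The concern.** A PPI term measures how coupling with the seed changes between conditions. A run with one unbroken condition has nothing for the coupling to change between. The plan nevertheless calls for a resting PPI and, in two separate sentences, makes a resting interaction the source of the regression predictor. No other section offers a different resting model or a rule for selecting resting clusters.

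The resting half of two stated hypotheses depends on this. Rest is not incidental to the imaging aim: the imaging paragraph under Power and Sample Size opens with a study of resting prefrontal-amygdala connectivity (effect size 0.8). If the text stays as it is, whoever analyses the scans must decide on the estimate, the region and the cluster rule unaided, possibly with the clinical outcomes already known.

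**Working it through.** The plan states no figure here, so there is none to reproduce. The check is whether the plan's own model can deliver the resting estimate it names.

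**Inputs.** From the analysis text: task vector T, amygdala series S, and the terms +T·S and -T·S. I add an intercept, which makes five columns: 1, T, S, T·S, -T·S, with coefficients b1 to b5. From the Neuroimaging Component: a cue run has two 3-minute blocks (T = 1, then -1, convolved with the haemodynamic response); rest has no conditions. T at rest is not given, so I take the two codings that express no change of condition, T = 0 and T = 1.

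**Target.** Because b4·(T·S) + b5·(-T·S) = (b4 - b5)·T·S, the interaction is θ = b4 - b5.

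**Cue run.** The columns 1, T, S and T·S are independent, and -T·S repeats one of them with the sign reversed. Rank is 4 of 5 and θ is estimable. The missing rank comes only from entering the interaction twice and does no harm.

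**Rest, T = 0.** The columns are 1, 0, S, 0, 0, so rank is 2 of 5. The fitted value is b1 + b3·S. θ does not appear and has no estimate. The seed coefficient b3 is estimable.

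**Rest, T = 1.** The columns are 1, 1, S, S, -S, so rank is 2 of 5. The fitted value is (b1 + b2) + (b3 + θ)·S. Only the sum b3 + θ is identified; neither the interaction nor the seed coefficient can be separated from it.

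**Rest, cue waveform borrowed.** This coding makes θ estimable, so I looked at what it returns. In 2,000 simulated resting runs with constant coupling of 0.5, the interaction averaged -0.001 (SD 0.070) and the seed coefficient averaged 0.500. The interaction correctly reports no change, and so says nothing about the level of resting connectivity. Assumptions: 180 volumes (6 min × 60 s ÷ 2 s, taking the stated TR to hold at rest), seed autocorrelation 0.4, unit-variance noise.

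**Rest, seed-only model.** The columns are 1, S; rank is 2 of 2 and the coefficient is estimable.

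| Run and coding | Rank | Interaction estimable | Seed coefficient estimable |
|---|---|---|---|
| Cue run, 1/-1 | 4 of 5 | yes | yes |
| Rest, T = 0 | 2 of 5 | no | yes |
| Rest, T = 1 | 2 of 5 | no | no |
| Rest, seed-only | 2 of 2 | not in model | yes |

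The ranks for T = 0 and T = 1 do not depend on the TR, the number of volumes or the simulated seed.

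**Extent.** The predictor sets are rest and alcohol cue in 3A, and rest and trauma cue in 3B: 4 in all, of which the 2 resting sets are affected.

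**The case against.** **The wording may be loose rather than wrong.** The reference to rest could attach to the parameter estimate instead of the interaction. Clusters would then come from the cue contrast, the only one described, and resting values would be read at the same voxels. The plan also introduces PPI as a seed-based measure of functional coupling, so an imaging analyst might assume that ordinary seed connectivity was intended. That may well be the intention. But the plan expressly lists rest among the PPI analyses, and even the generous reading does not say which resting estimate is to be read, because the only model described needs a task vector. The ambiguity is real, and it still needs an edit.

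**Software may return a usable number anyway.** With a constant task and a minimum-norm solution, write β for the seed-only coefficient. Then b3 + b4 - b5 = β is met by b3 = b4 = β/3 and b5 = -β/3, so θ = 2β/3. The outcome regression would then in effect test resting connectivity. This is true, but it depends on solver behaviour that the plan does not mention and is not estimation in the ordinary sense. It does rule out saying that following the text must yield nothing usable.

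**Stronger readings to avoid.** A reader might infer that the model already outputs the right resting measure and the regressions merely pick the wrong image. The documents do not support that: the seed image is clean only if T = 0, a coding the plan never states, and under a constant task it is aliased with the interaction. A reader might also suppose that the task is a constant convolved with the haemodynamic response, and conclude that the predictor reflects only the opening seconds of the run. That coding makes the interaction formally estimable, but no section proposes it, so conclusions drawn from it concern a model the plan does not contain.

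**Conclusion.** The concern stands in this form: the plan prescribes, for the resting run, an estimate that its own definition and model leave undefined. The resting half of 3A and 3B, 2 of 4 predictor sets, cannot be tested as written. This goes beyond missing detail, because the analysis that is stated cannot supply the predictor the hypotheses name.

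The conclusion rests on the description of rest as a single condition and on the absence of any task vector or group contrast for it. The simulation is illustrative only. A reader might infer that Aim 3 as a whole fails. It does not: the cue-run PPI is estimable, and neither Aims 1 and 2 nor any sample-size figure is affected. It should be corrected before the imaging data are related to outcomes.

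**What to change.** For the resting run, replace the PPI model. Suggested content:

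- **Model.** Regress each voxel's resting series on the amygdala time series plus nuisance terms, with no task or interaction term.
- **Predictor.** Use the seed coefficient from the baseline scan, or the Fisher-z transformed correlation. Name one.
- **Location.** Read it either in a prefrontal region fixed before analysis, or in prefrontal clusters from the resting group seed map under the existing rule (Z > 2.3, corrected cluster p = 0.05). Either is workable; state the choice in advance. The existing threshold already covers all group-level results, so the second option needs no new rule.
- **Regressions.** Regress change in total standard drinks (3A) and change in CAPS-5 total score (3B) on that value.
- **Text.** Remove rest from the list of PPI analyses and from the two interaction-cluster sentences. Keep PPI for the alcohol and trauma runs as planned.

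The cost is a revision of the analysis text and scripts, plus committing beforehand to the region or the cluster rule. No new scans or data are needed.
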